16.1.2. Definition of Myocardial Infarction

Different criteria for spontaneous and peri-procedural MI will be utilized.

• **Spontaneous MI** (occurring >72 hours after any PCI or CABG)

Detection of rise and/or fall of cardiac biomarkers (CK-MB or troponin) with at least one value

above the upper reference limit (URL)* together with evidence of myocardial ischemia with at least one of the following:

- ECG changes indicative of new ischemia [ST-segment elevation or depression as defined below, in the absence of other causes of ST-segment changes such as left ventricular hypertrophy (LVH) or bundle branch block (BBB)] *or*
- Development of pathological Q waves (≥ 0.04 seconds in duration and ≥ 1 mm in depth) in ≥ 2 contiguous precordial leads or ≥ 2 adjacent limb leads) of the ECG, *or*
- Angiographically documented graft or native coronary artery occlusion or new severe stenosis with thrombosis and/or diminished epicardial flow, *or*
- Imaging evidence of new loss of viable myocardium or new regional wall motion abnormality

*If the upper reference limit (URL) from the respective laboratory performing the assay is not available, then the URL for myocardial necrosis from the laboratory should be used. If the URL or the URL for myocardial necrosis is not available, the MI decision limit for the particular laboratory should be used as the URL. Reference limits from the laboratory performing the assay are preferred over the manufacturer's listed reference limits in an assay's instructions for use.

ST elevation

New ST elevation at the J point in two anatomically contiguous leads with the cut-off points: ≥ 0.2 mV in men (>0.25 mV in men <40 years) or ≥ 0.15 mV in women in leads V2-V3 and/or ≥ 0.1 mV in other leads

ST depression

New horizontal or down-sloping ST depression ≥ 0.05 mV in two contiguous leads.

The above ECG criteria illustrate patterns consistent with myocardial ischemia

• **Procedure-Related Myocardial Infarction** (occurring within 72 hours of either PCI or CABG)

In the present study it is essential to have an identical definition for MI after both PCI and Furthermore, given that MI represents one CABG to eliminate ascertainment bias. component of the primary composite endpoint of death, stroke or MI, and that death and stroke are devastating complications, only prognostically important MI that has clearly been associated with subsequent mortality will be included in the primary endpoint. In this regard, small levels of cardiac enzyme elevation after PCI reflect the underlying degree of atherosclerosis¹³⁵ and seem to have little or no prognostic significance, ^{136, 137} Large-scale studies in the stent era have shown that peak post-PCI levels of $\geq 8x$ the upper limits of normal ULN or $\geq 10x$ ULN are required before an association with subsequent mortality emerges,¹³⁸ although some studies have suggested that a CPK-MB of CPK-MB \geq 5x ULN may be prognostically important.^{137,139,140} Myocardial infarction may be difficult to diagnosis in the peri-surgical period given an obligate release of cardiac enzymes from all CABG procedures, although post CABG CPK-MB levels of ≥ 5 fold or ≥ 10 fold increased have been shown to be prognostically related to subsequent mortality.^{141,142,143,144} Moreover, cardiac troponin elevations after PCI are of uncertain prognostic importance, in contrast to

spontaneous troponin elevations in subjects with myonecrosis unrelated to revascularization procedures (spontaneous MI), for which numerous studies have shown to be strongly predictive of subsequent mortality.^{140,145,146,147,148,149,150} Thus, in the present study only CK-MB elevations will be used for determination of peri-procedural MI, whereas troponin or CK-MB elevations may be used to diagnose spontaneous MI.

CK-MB levels will be drawn at baseline and at 12 ± 2 hrs and at 24 ± 2 hrs post procedure (or at discharge if this occurs before 24 ± 2 hrs), and more frequently for signs or cardiac symptoms of clinical or hemodynamic instability. 12-lead EKGs will be recorded at baseline, within 24 hours after the procedure (at the same time as the CK-MB draw if possible) and at discharge.

The baseline CK-MB must be normal for subject enrolment in this study. A post procedure MI will be defined as the occurrence within 72 hours after either PCI or CABG of either:

- CK-MB above 10 x URL (*determined on a single measurement), OR
- CK-MB above 5 x URL (*determined on a single measurement), PLUS
 - new pathological Q waves in at least 2 contiguous leads or new persistent non-rate related LBBB, or
 - angiographically documented graft or native coronary artery occlusion or new severe stenosis with thrombosis and/or diminished epicardial flow, *or*
 - imaging evidence of new loss of viable myocardium or new regional wall motion abnormality

Symptoms of cardiac ischemia (which are of course difficult to assess in the post CABG patient either because of intubation or incisional pain) are not required for the diagnosis of peri-procedural MI.

For each MI identified by the CEC, the type of MI will also be described as:

- ST-Elevation MI (STEMI)
 - Also categorize as:
 - Q-wave**
 - Non-Q-wave
 - Unknown (no ECG or ECG not interpretable)
- Non-ST-Elevation MI (NSTEMI)
 - Also categorize as:
 - Q-wave**
 - Non-Q-wave
 - Unknown (no ECG or ECG not interpretable)
- Unknown (no ECG or ECG not interpretable)

** Development of new (i.e., not present on the subject's ECG before allocation) pathological Q-waves (≥ 0.04 seconds in duration and ≥ 1 mm in depth) in ≥ 2 contiguous precordial leads or ≥ 2 adjacent limb leads.

16.1.3. Definition of Stroke

Stroke is defined as the rapid onset of a new persistent neurologic deficit attributed to an obstruction in cerebral blood flow and/or cerebral hemorrhage with no apparent non-vascular cause (e.g., trauma, tumor, or infection). Available neuroimaging studies will be considered to support the clinical impression and to determine if there is a demonstrable lesion compatible with an acute stroke. Strokes will be classified as ischemic, hemorrhagic, or unknown.

All patients to be randomized into the Excel RCT will have a modified Rankin Scale (mRS) assessment conducted by mRS trained personnel at baseline and each visit and telephone interview. Additionally, the site research coordinator will evaluate each subject at 30 days, 6 months, 1, 2, 3, 4 and 5 Y follow-up time points and at the primary endpoint follow-up time point (either at annual follow-up or at subject contact for primary endpoint AE check) using a Transient Ischemic Attack (TIA)/Stroke Questionnaire and mRS Disability Questions (Appendix J). This questionnaire is a National Institute of Health Stroke Scale (NIHSS) validated questionnaire used in the CREST clinical trial. The mRS disability questions are adapted from a structured interview developed for stroke patients¹. If a subject's response to this questionnaire indicates a possible stroke or a change in the mRS, then a vascular neurologist or stroke specialist or a mRS certified personnel will confirm the mRS scale, determine whether a stroke has occurred and determine the stroke severity using the NIHSS TIA/Stroke questionnaire.

If a new stroke is diagnosed at the site, the investigators at the site will prepare a short narrative that describes the findings that support the diagnosis. All stroke events will be adjudicated by the Clinical Events Committee (CEC). Furthermore, if there is an increase in the mRS by one or more points noted at any visit, then an evaluation will be carried out to determine if a stroke or other outcome event has occurred. Post procedure, if a patient is diagnosed and adjudicated with a stroke event by the Clinical Events Committee (CEC), a disability assessment will be performed at least 90 days±2 weeks after the diagnosis of stroke using the mRS assessment instrument.

Any certification or mRS training for the personnel should be based on the structured interview version as in Appendix J (Modified Rankin Disability Questionnaire).

A. For the diagnosis of stroke, the following four criteria should be fulfilled:

- 1. Rapid onset* of a focal/global neurological deficit with at least one of the following:
 - Change in level of consciousness
 - Hemiplegia
 - Hemiparesis
 - Numbness or sensory loss affecting one side of the body
 - Dysphasia/Aphasia
 - Hemianopia (loss of half of the field of vision of one or both eyes)

¹ Wilson JTL, Hareendran A, Grant M, Baird T, Shultz UGR, Muir KW, and Bone I. "Improving the Assessment of Outcomes in Stroke: Use of a Structured Interview to Assign Grades on the Modified Rankin Scale." Stroke. 2002; 33; 2243-46.

- Amaurosis fugax (transient complete/partial loss of vision of one eye)
- Other new neurological sign(s)/symptom(s) consistent with stroke

*If the mode of onset is uncertain, a diagnosis of stroke may be appropriate provided that there is no plausible non-stroke cause for the clinical presentation

- 2. Duration of a focal/global neurological deficit ≥24 hours or<24 hours if any of the following conditions exist:
 - i. at least one of the following therapeutic interventions:
 - a. Pharmacologic (i.e., thrombolytic drug administration)
 - b. Non-pharmacologic (i.e., neurointerventional procedure such as intracranial angioplasty)
 - ii. Available brain imaging clearly documents a new hemorrhage or infarct
 - iii. The neurological deficit results in death
- 3. No other readily identifiable non-stroke cause for the clinical presentation (e.g., brain tumor, trauma, infection, hypoglycemia, other metabolic abnormality, peripheral lesion, or drug side effect). Patients with non-focal global encephalopathy will not be reported as a stroke without unequivocal evidence based upon neuroimaging studies.
- 4. Confirmation of the diagnosis by a neurology or neurosurgical specialist and at least one of the following:
 - a. Brain imaging procedure (at least one of the following):
 - i. CT scan
 - ii. MRI scan
 - iii. Cerebral vessel angiography
 - b. Lumbar puncture (i.e. spinal fluid analysis diagnostic of intracranial hemorrhage)
- B. If the acute focal signs represent a worsening of a previous deficit, these signs must have either
 - 1. Persisted for more than one week, or
 - 2. Persisted for more than 24 hours and were accompanied by an appropriate new CT or MRI finding
- C. Strokes may be sub-classified as follows:
 - 1. Ischemic (Non-hemorrhagic): a stroke caused by an arterial obstruction due to either a thrombotic (e.g., large vessel disease/atherosclerotic or small vessel disease/lacunar) or embolic etiology.
 - 2. Hemorrhagic: a stroke due to a hemorrhage in the brain as documented by neuroimaging or autopsy. This category will include strokes due to primary intracerebral hemorrhage (intraparenchymal or intraventricular), ischemic strokes with hemorrhagic transformation (i.e., no evidence of hemorrhage on an initial imaging study but appearance on a subsequent scan), subdural hematoma,* and primary subarachnoid hemorrhage.

*All subdural hematomas that develop during the clinical trial should be recorded and classified as either traumatic versus nontraumatic.

3. Unknown: the stroke type could not be determined by imaging or other means (e.g., lumbar puncture, neurosurgery, or autopsy) or no imaging was performed.

D. Stroke Disability

All strokes with stroke disability of Modified Rankin Scale (mRS) ≥ 1 will be

included in the primary endpoint. All diagnosed strokes (even with mRS 0) will also be tabulated. Stroke disability will be classified using an adaptation of the modified Rankin Scale as follows, the assessment of which will be based on the Modified Rankin Disability Questionnaire (Appendix J.)

Scale	Disability	
0	No stroke symptoms at all. (May have other complaints)	
1	No significant disability; symptoms present but no physical or other limitations.	
2	Slight disability; limitations in participation in usual social roles, but independent for activities of daily living (ADL)	
3	some need for assistance but able to walk without assistance	
4	Moderately severe disability; need for assistance with some basic ADL, but not requiring constant care	
5	Severe disability; requiring constant nursing care and attention.	
Stroke: Modified Rankin score ≥ 1 and increase by ≥ 1 from baseline		

- E. Transient Ischemic Attack (as compared to stroke) is defined as:
 - New focal neurologic deficit with rapid symptom resolution, usually 1-2 hours, always within 24 hours
 - Neuroimaging without tissue injury

16.1.4. Definition of Coronary Revascularization Procedures

A coronary revascularization procedure may be either a coronary artery bypass graft (CABG) surgery or a percutaneous coronary intervention (PCI) (for example, angioplasty, stenting), regardless of procedural success.

Coronary revascularization procedures may be further classified as follows:

- Urgent: an urgent procedure is one that is performed within 48 hours of upon diagnosis of the subject's status due to urgency of the medical condition, but is not otherwise considered emergent
- Emergent: an emergent procedure is one that is performed as soon as possible (usually within 6 hours)
- Elective: an elective procedure is one that is scheduled and is not urgent or emergent

Procedural Success may be defined as follows:

• CABG: the successful placement of at least one conduit with either a proximal and distal anastomosis or a distal anastomosis only

• PCI: successful balloon inflation with or without stenting and the achievement of a residual stenosis <50% of the left anterior descending coronary artery and/or the left circumflex artery. The balloon inflation and/or stenting could have been preceded by adjunctive device use (e.g., Angiojet, rotational atherectomy etc.)

Target Lesion: A lesion revascularized in the index procedure (or during a planned or provisional staged procedure). The LM target lesion extends from the left main stem ostium to the end of the 5 mm proximal segments of the left anterior descending and left circumflex arteries as well as the ramus intermedius if the latter vessel has a vessel diameter of ≥ 2 mm.

Target Vessel: The target vessel is defined as the entire major coronary vessel proximal and distal to the target lesion including upstream and downstream branches and the target lesion itself. The left main and any vessel originating from the left main coronary artery or its major branches is, by definition, considered a target vessel for the purposes of this trial (unless either the LAD or LCX are occluded at baseline and no attempt was made to revascularize these territories by either PCI or CABG).

Target Vessel-Non-Target Lesion: The target vessel but non-target lesion consists of a lesion in the epicardial vessel/branch/graft that contains the target lesion; however, this lesion is outside of the target lesion by at least 5 mm distal or proximal to the target lesion determined by quantitative coronary angiography (QCA)

Non-Target Vessel: For the purposes of this trial, the only possible non-target vessel would be the right coronary artery and its major branches that were not treated by either PCI or CABG at the index procedure (unless either the LAD or LCX are occluded at baseline and no attempt was made to revascularize these territories by either PCI or CABG).

Target Vessel Revascularization (TVR): Target vessel revascularization is any repeat percutaneous intervention of the target vessel or bypass surgery of the target vessel

Target Lesion Revascularization (TLR): Target lesion revascularization is defined as any repeat percutaneous intervention of the target lesion or bypass surgery of the target vessel

All revascularization events will be adjudicated as either ischemia-driven or non ischemiadriven

Ischemia-Driven Target Lesion (or Vessel) Revascularization: A target lesion (vessel) revascularization will be considered ischemia-driven if the target lesion diameter stenosis is \geq 50% by QCA (analysis segment measurement, involving the lesion itself and 5 mm of proximal and/or distal margin) and any of the following criteria for ischemia are met:

- A positive functional study corresponding to the area served by the target lesion; or
- Ischemic ECG changes at rest in a distribution consistent with the target vessel; or
- Typical ischemic symptoms referable to the target lesion; or
- IVUS of the target lesion with a minimal lumen area (MLA) of ≤4mm² for non left main lesions or ≤6mm² for left main lesions. If the lesions are *de novo* (i.e. not restenotic), the plaque burden must also be ≥60%; or
- FFR of the target lesion ≤ 0.80
Note: A target lesion revascularization for a diameter stenosis less than 50% might also be considered ischemia-driven by the CEC if there was a markedly positive functional study or ECG changes corresponding to the area served by the target lesion.

Ischemia-Driven Non-Target Vessel Revascularization: A non target vessel revascularization will be considered ischemia-driven if any lesion the non target vessel has a diameter stenosis \geq 50% by QCA with any of the above criteria for ischemia met.

Unplanned revascularization for ischemia: Any repeat revascularization of either a target vessel or non-target vessel with any of the above criteria for ischemia met.

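### Section 16.1.4 judges whether a repeat target vessel revascularization is ischemia-driven by the lesion treated at index, not by the lesion treated at the repeat procedure

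*Protocol*

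**What the plan says.** All the definitions are in Protocol section 16.1.4.

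- Target lesion: "A lesion revascularized in the index procedure (or during a planned or provisional staged procedure"). For the left main it runs from the ostium to the end of the first 5 mm of the LAD and LCX (and of a ramus of at least 2 mm).
- Target vessel: "The left main and any vessel originating from the left main coronary artery or its major branches is, by definition, considered a target vessel", except an LAD or LCX that was occluded at baseline and not attempted.
- A separate category exists for disease in a target vessel but away from the treated lesion: "this lesion is outside of the target lesion by at least 5 mm distal or proximal to the target lesion".
- Ischemia-driven TLR and TVR share one rule: "A target lesion (vessel) revascularization will be considered ischemia-driven if the target lesion diameter stenosis is" at least 50% by QCA, plus at least one of five ischemia criteria. Four are worded for the target lesion, for example "A positive functional study corresponding to the area served by the target lesion; or". Only the rest ECG criterion is worded for the vessel: "Ischemic ECG changes at rest in a distribution consistent with the target vessel; or".
- A note lets the CEC accept a stenosis below 50%, but only for target lesion revascularization.
- For a non-target vessel, the 50% threshold may be met by any lesion in that vessel, and the same ischemia criteria then apply.
- Unplanned revascularization for ischemia is "Any repeat revascularization of either a target vessel or non-target vessel with any of the above criteria for ischemia met".

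The last item is a component of the second powered secondary endpoint, tested for non-inferiority with a margin of 8.4 points at one-sided alpha 0.05 (SAP 2.3.2, 2.5.2 and 3.10).

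**The concern.** The category of target vessel, non-target lesion is defined but has no test of its own. A repeat procedure on such a lesion is TVR, and its classification depends on a different lesion, the one treated at index. The state of that index lesion differs systematically by arm. After successful PCI it is open; after CABG it is bypassed but still there.

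At stake are the accuracy of ischemia-driven TVR and, to a lesser and less certain extent, the revascularization component of the second powered secondary endpoint. In a non-inferiority comparison, a net loss of PCI events would favor the conclusion being tested.

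**Working it through.** **1. A worked case against the text.** A subject had left main PCI. The stent is patent, so the target lesion is below 50%. A new mid-LAD lesion causes angina, has a positive FFR and is stented. It lies beyond the first 5 mm of the LAD and no lesion there was treated at index, so this is TVR on a non-target lesion.

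- 50% threshold: measured at the target lesion; not met.
- CEC note for stenosis below 50%: limited to target lesion revascularization; not available.
- Symptoms, IVUS, FFR: those of the new lesion, not of the target lesion; not met.
- Functional study: a left main lesion serves LAD and LCX territory, so a positive study could meet this criterion.
- Rest ECG: keyed to the target vessel, so changes could meet this criterion.

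So the procedure fails the ischemia-driven TVR rule through the threshold, whatever the criteria show. On the criteria alone it fails when the evidence is symptoms, IVUS or FFR only. That is a foreseeable pathway. Section 8.3.1 steers subjects with typical angina to catheterization rather than stress testing, and section 8.3.3 prefers FFR for non-left-main lesions.

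**2. The same procedure after CABG.** The grafted native lesion remains. Entry required at least 50% stenosis by visual estimate, or left main equivalent disease (section 6.5.1), so the QCA threshold will usually still be met whatever lesion is treated. An ischemia criterion is still needed.

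**3. Conflict with other text.** Section 8.3.3 sets its conditions for repeat intervention for lesions treated earlier and for new ones. The non-target-vessel rule accepts any lesion for the threshold, then imports criteria that name the target lesion or target vessel. An untreated RCA contains neither, so it cannot literally meet them.

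**4. What reaches the powered composite.** The TLR/TVR rule has two parts, a threshold and a list of ischemia criteria. The non-target-vessel rule restates a threshold. Unplanned revascularization for ischemia restates none and asks only for the criteria. The target-lesion wording of the criteria therefore carries over; the threshold does not clearly do so.

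**5. The plan's own figure.** Inputs (Protocol 9.1.6.2, SAP 2.5.2): 22% per arm, margin 0.084, one-sided alpha 0.05, 950 per arm, 8% loss. 950 × 0.92 = 874.

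- SE = sqrt(2 × 0.22 × 0.78 / 874) = 0.0198.
- Power = Φ(0.084/0.0198 − 1.645) = 99.5% (99.7% with 950 per arm).
- With a Kaplan-Meier variance (29 months of uniform accrual, 2-year minimum follow-up, 8% loss): 99.3%.

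The stated power of about 99% is reproduced.

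**6. Illustration of size.** Suppose the true rates are 30.4% (PCI) and 22% (CABG), exactly the margin apart, and a net x of PCI events goes uncounted. Then

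P(declare non-inferiority) = Φ(x/SE − 1.645), with SE = sqrt[(0.304 − x)(0.696 + x)/874 + 0.22 × 0.78/874].

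- x = 0: 5.0%.
- x = 0.01: SE = 0.0208, Φ(0.480 − 1.645) = 12.2% (Kaplan-Meier variance 11.9%).
- x = 0.02: SE = 0.0207, Φ(0.966 − 1.645) = 24.8% (Kaplan-Meier variance 23.9%).

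Against the planning rates, 1 to 2 points is 9% to 18% of the 22 − 11 = 11 points that come from revascularization alone. If both arms lose the same number of points, the difference stays at 8.4 and the error stays at 5%.

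**The case against.** The literal reading may not be what was meant. Applied to non-target vessels it makes most of the criteria impossible to meet. The IVUS criterion also makes special provision for de novo, non-restenotic lesions, which fits the lesion at issue better than a stented one. The CEC works from a separate manual (section 8.6) that is not among the documents and may already apply the test to the treated lesion. This stands as a limit on what can be concluded about adjudication in practice. It does not repair the protocol text, which defines a component of a powered endpoint.

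The exposed cases are also narrower than all new lesions. Functional and ECG evidence can still qualify, and repeat percutaneous TLR is largely unaffected because the treated lesion is then the target lesion. All revascularization, whatever its cause, is a separate secondary endpoint (SAP 2.3.3) and captures every one of these procedures. These points stand and reduce the stakes.

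A reader might infer more: that in the powered composite, PCI procedures drop out while CABG procedures count by default, so non-inferiority is biased by a known amount. The documents do not support that.

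- The threshold, which is what separates the arms most clearly, is not restated for the composite's component.
- The target-lesion wording of the criteria binds both arms. A new native or graft lesion after CABG, shown only by its own FFR or symptoms, fails it too.
- Meeting the threshold after CABG is usual rather than automatic, because entry is visual and the threshold is by QCA.
- Persistence of the index IVUS finding is not enough in general. The criterion adds a plaque burden of at least 60% for de novo lesions, which entry on lumen area does not require.

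A difference between arms remains plausible. Section 7.5 asks for grafting of all stenoses of at least 50% in arteries of at least 1.5 mm, but strongly recommends PCI only of ischemia-producing lesions, so what counts as a target lesion differs by arm. Neither its size nor its net direction in the composite can be derived from the documents.

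**Conclusion.** The rule in section 16.1.4 names the wrong lesion for target-vessel, non-target-lesion procedures and should be corrected. The effect on ischemia-driven TVR is clear from the text. For the second powered secondary endpoint, the target-lesion wording of the criteria carries over and could lose events in both arms; whether the 50% threshold applies there is unclear. The 12% to 25% error is an illustration. It assumes a net 1 to 2 points lost from PCI only, a true excess equal to the margin, 874 per arm and a normal approximation. No document gives the affected share. The primary endpoint of death, MI or stroke, and study success (SAP 2.7), are not affected.

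**What to change.** In section 16.1.4, state the 50% threshold and every ischemia criterion for the lesion or graft treated at the repeat procedure, or the territory it supplies. Use the same wording in both arms for TVR, non-TVR and unplanned revascularization for ischemia. State whether the 50% threshold applies to the last of these. Bring the CEC manual into line.

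The cost is a wording change in two documents. Section 8.2 already sends all follow-up angiograms to the core laboratory, so no new data are needed. If events have already been adjudicated under the current text, a limited CEC re-review is needed. Because the trial is unblinded, it should be done without knowledge of results by arm. Sample size, margin and power stay as they are.
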